#### **Data Collection:**

Data collected will include: demographics, past medical history, hospital information including

initial resuscitation information and post-operative care, complications (**Appendix A**), and discharge information. A list of the data elements to be collected can be found in Appendix A. Data will be collected from the subject's medical record and the trauma registry. Risk/Safety evaluation will be performed at half enrollment (at 13 enrolled and randomized patients).

All subjects enrolled in this study will be assigned a study specific number. The de-identified data will be entered into a secure, password protected database accessible to only those involved in the study. A study linking log which will link subject identifiers to the study number will be kept by the study PI.

To ensure patient confidentiality is maintained at all times, all data will be maintained in accordance with HIPAA rules and regulations. Hard copy source documentation will be kept in a secure area in a locked office and electronic data will be stored on secure, password-protected computers accessible to only those study specific personnel.

**Outcomes - Biomarkers of Endothelial and Glycocalyx Injury:** The primary outcome is a reduction in serum biomarkers associated with glycocalyx breakdown (syndecan-1, sTM), endothelial leakage (sFLT-1, VEGF, sTM), sympatho-adrenal activation (NE, epinephrine), and inflammation (VEGF, sRAGE, HMGB-1, IL-6, 8, 10, 1 $\alpha$ , 1 $\beta$ ) in the plasma group. A rodent model has shown evidence of glycocalyx restoration after 2 hours of resuscitation with plasma as compared to crystalloid. Biomarkers will be drawn at 0, 2, end of initial bolus of fluid administration, 6, 12, and 24 hours to evaluate their trend in response to plasma versus crystalloid resuscitation. Timing of biomarker lab draw at the end of the initial fluid bolus will be variable since termination of fluid resuscitation depends on patients' clinical response. Lactic acid will be drawn per standard of care to guide resuscitation. Standard labs for critically ill patients (such as complete blood count, basic metabolic panel, and arterial blood gases) will be obtained per STICU protocol. See **Table 2** for timing of biomarker lab draws. Funding for measuring biomarkers will be obtained from an additional source if the grant is awarded.

Table 2: Timing of Lab Draws Upon Randomization (T=0) in hours						
	T = 0	T = 2	T = EoR	T = 6	T = 12	T = 24
Serum Biomarkers	✓	✓	✓	✓	✓	✓

Serum biomarkers = syndecan-1, sTM, sFLT-1, VEGF, sRAGE, HMGB-1, IL-6, 8, 10, 1 $\alpha$ , 1 $\beta$ , vWF, tPA, NE, and epinephrine;  
EoR = End of Resuscitation (variable, depending on patient response to fluids)

resuscitation, time on vasopressors, time until lactate normalization, ventilator days, ICU-free days, and hospital length of stay. Organ dysfunction will be measured including acute lung injury and acute renal failure. Standardized definitions will be used as outlined in the method of operation used in previously conducted trials by our group. Potential harms of plasma administration will be assessed including symptomatic and asymptomatic venous thromboembolisms, transfusion-related allergic reactions, febrile non-hemolytic transfusion reaction, delayed-serological transfusion reactions, and transfusion-associated circulatory overload. Risk/safety evaluation will be performed at half recruitment (13 randomized patients).

**Blinding:** The healthcare provider will not be able to be blinded to the study intervention. The outcome assessors will be blinded when feasible, and the laboratory technicians and statisticians will be blinded.

**Sample Size:** We propose to enroll 26 patients (13 in each treatment arm) for the pilot randomized study to obtain unbiased estimates of treatment effect. We propose to enroll up to 100 patients to the observational study arm. Because this is a feasibility pilot study, we do not provide a power analysis for any outcomes since no formal hypothesis testing will be conducted. Instead, we will calculate estimates of treatment effect and 95% confidence intervals for all measures. We will also calculate probabilities of treatment benefit/harm using Bayesian analyses and conservative neutral priors. These estimates will inform the design of a future larger trial.

**Statistical Analysis:** Because this is a pilot, efficacy trial, we will perform both a per-protocol and an intention-to-treat analysis. Both frequentist and Bayesian analysis will be performed. For the primary outcome and all continuous outcomes (using variable transformations if needed), we will use mixed models that include group and time period as covariates with a random subject effect. We will report group differences and 95% CIs from these models. For binary outcomes, a log binomial (or Poisson in case of non-convergence) will be used to estimate relative risks and 95% CIs. Hazard ratios and 95% CIs will be reported for time-to-event comparisons. For the Bayesian analysis, neutral conservative priors (that exclude large treatment effects almost never seen with medical interventions) will be used to estimate the probability of both benefits and harms, as defined by our primary and secondary outcomes.

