### Background:

Sepsis and septic shock are a major worldwide public health problem. Although implementation of the evidence-based Surviving Sepsis Guidelines has resulted in improvement in sepsis-related deaths, in-hospital mortality continues to range from 12-40%. The guidelines provide strong recommendations for initial resuscitation with crystalloids – 30 mL/kg within the first 3 hours. However, the guidelines state that there is “little available evidence from RCTs to support its practice; this is an area in which research is urgently needed”. Randomized trials have primarily compared crystalloids to colloids and have not evaluated the recommended fluid volume. Furthermore, there is observational data from large administrative databases that increased fluid administration in the first 24 hours increases mortality.

**Figure 1:** Conceptual model of how septic shock leads to sympathoadrenal activation, inflammation, and ischemia, which affects the endothelial glycocalyx, endothelial permeability, and hemostatic balance, resulting in edema and microcirculatory disturbances that cause organ dysfunction

Abbreviations: sTM = soluble thrombomodulin; sFLT-1 = soluble fms-like tyrosine kinase-1; VEGF = vascular endothelial growth factor; sRAGE = soluble receptor for advanced glycation endproduct; HMGB-1 = high mobility group protein-1; IL = interleukin; vWF = von Willebrand factor; tPA = tissue plasminogen activator; NE = norepinephrine; rTEG = rapid thromboelastogram

\*indicates biomarkers that belong to more than 1 category

Recently, shock-induced endotheliopathy (**SHINE**) has been proposed as a shared pathophysiologic mechanism associated with worsened outcomes in patients with critical illness including trauma and sepsis. Activation of the sympathoadrenal system and release of catecholamines due to acute injury (i.e., sepsis or trauma) leads to breakdown of the glycocalyx, or the network of membrane-bound proteoglycans and glycoproteins that covers the endothelium (**Figure 1**). This has been associated with capillary leakage and microvascular thrombosis, ultimately resulting in organ dysfunction and increased mortality. Research suggests that

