**Table 1 – The Sepsis Screening Score**

This cutoff has a negative predictive value of 96%, which would rule out the majority patients without sepsis. Enrolled patients will be randomized only if they meet criteria for septic shock: 1) hypotension with MAP < 65 mmHg, and 2) evidence of hypoperfusion including lactic acid > 2.2 mmol/L, altered mental status, or decreased urine output of < 0.5 mL/kg in the past hour.

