**Endpoints of Resuscitation:** Fluid resuscitation in both the intervention and the control arms will be titrated to serial reassessments of the patient's volume status via blood pressure monitoring (MAP > 65 mmHg), urine output measurements (goal of  $\geq 0.5$  cc/kg/hr), CVP measurements (>8 mmHg), stroke-volume variation on hemodynamic monitors (such as the Vigileo), inferior vena cava (IVC) collapsibility index via bedside ultrasound, and lactate clearance (goal of  $\geq 50\%$  clearance after 6 hours of resuscitation). Serial laboratory examinations including lactate levels will be performed per standard of care in the ICU, until the lactate has normalized. Additional fluid support after the initial plasma or crystalloid bolus will be given at the discretion of the treating clinician, keeping in mind that septic shock patients in several randomized trials required 6-8L crystalloid per day.

**Co-interventions:** Both groups will receive standard care following Surviving Sepsis Guidelines, including procurement of blood cultures, administration of broad-spectrum antibiotics, transfusion of packed red blood cells for hemoglobin < 7 mg/dL, and use of vasopressors to maintain MAP > 65 mmHg.

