### Hospital Information

- Admission date/time (ED and STICU/SIMU)
- Time of injury
- Type of injury
- Pre-hospital treatment (LSIs)
- Initial resuscitation therapy (blood products, IR, OR, LSIs)
- Vital signs
- Degree of pretibial edema
- Laboratory results
- Diagnostic procedure results
- Daily STICU/SIMU data ( i.e. ventilator settings, vital signs)
- Vasopressor use (medication, dose)
- Blood products and fluids
- Sepsis diagnostic information
- Operative and endovascular interventions
- Complications (ARDS, AKI, venous thromboembolic events, sepsis, severe sepsis, septic shock, transfusion reactions, infections, multi-organ failure, pneumonia)

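### Serum norepinephrine and epinephrine are primary-outcome markers, but the plan has no rule for samples drawn while either may be infused as a vasopressor

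*Combined protocol and SAP*

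**What the plan says.** - **Primary outcome** (Outcomes - Biomarkers of Endothelial and Glycocalyx Injury): "The primary outcome is a reduction in serum biomarkers associated with glycocalyx breakdown", followed by further marker groups, one of which is "sympatho-adrenal activation (NE, epinephrine". The Figure 1 abbreviations confirm "NE = norepinephrine". Draws are scheduled at 0 and 2 hours, at the end of the first bolus, and at 6, 12 and 24 hours.
- **Population** (text under Table 1): "Enrolled patients will be randomized only if they meet criteria for septic shock", there defined as low MAP plus a sign of hypoperfusion.
- **Co-interventions:** "Both groups will receive standard care following Surviving Sepsis Guidelines", including "use of vasopressors to maintain MAP > 65 mmHg". No vasopressor is named and none is ruled out.
- **Other outcomes** (text after Table 2): "time on vasopressors" is listed as an outcome.
- **Appendix A, Hospital Information:** "Vasopressor use (medication, dose") is collected, with no stated link to the times of the blood draws.
- **Statistical Analysis:** the mixed model has terms for arm and period plus a subject random effect. It has no provision for samples taken during an infusion. Bayesian probabilities of benefit and harm are to be computed on the primary and secondary outcomes.
- **Blinding:** treating staff know the allocation; laboratory technicians and statisticians do not.

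**The concern.** Two of the analytes that define the primary outcome are also drugs that the co-intervention rule permits. The assay reads total serum concentration. While the same substance is being infused, that total no longer isolates the body's own release, which is what the marker is meant to represent. Blinding the laboratory does not help, because the drug is already in the sample.

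The stake is the interpretation of the mechanism. The Background places sympatho-adrenal activation at the start of the endotheliopathy pathway, Aim 1 names it, and the Preliminary Data cite attenuated norepinephrine in rats given plasma. A lower norepinephrine reading in the plasma arm would naturally be taken as support for the pathway even if it came only from less infused drug. Equally, a real fall in endogenous release could be masked by more infused drug. Either result would enter the benefit and harm probabilities and the design of the later trial.

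**Working it through.** **1. How many markers are affected.** The distinct analytes in the primary-outcome sentence are syndecan-1, sTM, sFLT-1, VEGF, norepinephrine, epinephrine, sRAGE, HMGB-1, IL-6, IL-8, IL-10, IL-1α and IL-1β, which makes 13 (sTM and VEGF each appear twice). Two are affected and 13 − 2 = 11 are not. The two are the whole of their category.

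**2. The plan's own figures.** The randomized sample agrees with its block structure: 5 × 4 + 1 × 6 = 26, or 13 per arm. No alpha, power, effect size or SD is given, so there is no sample-size figure to recompute and this point changes none.

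**3. Can infusion exposure differ by arm?** From the Intervention and Control paragraphs:
- Plasma: 10 mL/kg at 2–3 mL/kg/hr. By 3 hours this is 3 × 2 = 6 to 3 × 3 = 9 mL/kg, and the full dose takes 10/3 = 3.3 to 10/2 = 5 hours.
- Crystalloid: 30 mL/kg within 3 hours.

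Either may be stopped early. The early volumes differ by a factor of 30/9 = 3.3 to 30/6 = 5 if run as planned, and unblinded clinicians give the vasopressors. Exposure could therefore differ, but the documents do not say in which direction.

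**4. Effect on the contrast (illustration; the fold-rise and the gap are assumptions).** Suppose endogenous release is identical in both arms and an infusion multiplies the reading by *f*. Let the share of patients on infusion at a draw be *p*P (plasma) and *p*C (crystalloid). On the log scale:

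spurious geometric mean ratio = *f*^(*p*P − *p*C)

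| *f* | no gap | plasma 10 points lower | plasma 20 points lower | plasma 20 points higher |
|---|---|---|---|---|
| 3 | 1.00 | 0.90 | 0.80 | 1.25 |
| 10 | 1.00 | 0.79 | 0.63 | 1.58 |
| 30 | 1.00 | 0.71 | 0.51 | 1.97 |

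**5. Chance imbalance at 13 per arm.** Take the number on infusion in each arm as independent binomial (13, *p*) with the same true *p*. The probability that the arms differ by 3 or more patients is 0.32 at *p* = 0.4 or 0.6, and 0.22 at *p* = 0.8. A 3-patient gap is 3/13 = 23 points. At *f* = 10 it gives 10^(−3/13) = 0.59, or 10^(3/13) = 1.70 the other way. This part is noise, which a confidence interval for the total level would reflect. It is not systematic bias, but the observed ratio still could not be read as a change in endogenous release.

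**6. What was not calculated.** An absolute infused concentration would need infusion rates, clearance and an endogenous level for comparison. The documents give none of these, so nothing here rests on one.

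**The case against.** The strongest reply is that this is a 26-patient pilot without formal testing. No composite is defined and no rule requires these two markers to fall, so at worst two of 13 estimates are misread. That stands as a reason for moderate severity. It does not remove the point, because benefit and harm probabilities are still attached to the primary outcome.

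It can also be said that the randomized comparison of total serum level remains valid. That is correct: what fails is the label of sympatho-adrenal activation for samples drawn on infusion.

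A third reply is that flagging alone would suffice, with both markers kept as primary. Flagging addresses interpretation, but the primary-outcome probabilities would still be computed on a mixture of drug and hormone.

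A reader might infer four stronger claims that the documents do not support:
- **That the whole sympatho-adrenal component measures the infusion.** Agents and exposure are not stated, and draws with no catecholamine infusion contributing to the sample are unaffected.
- **That the bias favours plasma.** The fluid schedules differ, both arms share one MAP target, and the direction is unknown.
- **That one event is counted twice, through serum norepinephrine and time on vasopressors.** They are separate outcomes that are never combined; being correlated is not double counting.
- **That every randomized patient is hypotensive.** The Inclusion Criteria allow randomization on any one listed sign, whereas the text under Table 1 requires low MAP plus hypoperfusion. Those passages must be reconciled, but the point here needs only that some patients receive a catecholamine infusion.

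**Conclusion.** The concern holds as a limit on interpretation. The plan names norepinephrine and epinephrine as primary markers of sympatho-adrenal activation, permits vasopressors in both arms without naming or excluding agents, and has no rule for samples drawn during an infusion. For those samples, a difference between arms cannot be attributed to endogenous release. The error could create or hide a reduction.

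Its reach is 2 of 13 primary markers. Its size is unknown: under the assumed 3- to 30-fold rise and a 20-point gap in infusion share, the spurious ratio is 0.80 to 0.51, or 1.25 to 1.97 with the gap reversed; with no gap it is 1.00. The conclusion assumes that norepinephrine or epinephrine is among the agents used, which the text permits but does not state. This should be fixed, but it does not undermine the trial as a whole.

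**What to change.** 1. In the primary-outcome paragraph, move norepinephrine and epinephrine to exploratory outcomes. Keep measuring them at every draw for Aim 1.
2. At each draw, record whether a catecholamine infusion is running, with agent and rate, by time-matching the vasopressor data already listed in Appendix A.
3. Report the two markers by arm and draw with on-infusion samples flagged, and state that no conclusion about endogenous activation is drawn from those samples.
4. Do not adjust for vasopressor dose: it is set after randomization and may itself be affected by treatment.
5. State that being on or off infusion is also determined after randomization, so comparisons between arms restricted to off-infusion samples are selected and only descriptive.

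**Cost.** A wording change, and infusion status for at most 26 × 6 = 156 draws in the randomized patients. Appendix A lists agent and dose but not their timing against the draws, so the matching is a small amount of extra work, best done as samples are taken. The trial loses two primary markers and has fewer interpretable catecholamine samples. No change to vasopressor management is implied.

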#### **Informed Consent:**

Exception from Informed Consent will not be used in this trial. Written informed consent will be obtained from potential subjects or a legally authorized representative prior to randomization.

**Randomization:** Randomization will occur once the informed consent has been obtained. A 1:1 allocation will be used for the randomization. Subjects will be randomized to either the intervention arm (use of plasma) or the control arm (standard of care). Randomization will be performed using a computer-generated random sequence placed in opaque, consecutively-numbered, sealed envelopes kept in the locked Center for Translational Injury Research (CeTIR) office. A CeTIR research coordinator is available 24 hours a day, 7 days a week. Allocation will be 1:1. Patients will be stratified by enrollment location (STICU, ED, and Medical) in 5 blocks of 4 and 1 block of 6 for a total of 26 patients. **[Figure 4].**

**Figure 4** – Flow diagram depicting patient screening, enrollment, and randomization.

**Intervention:** Initial resuscitation with plasma will be 10 mL/kg (700 mL in a typical 70 kg adult). Traditional doses of plasma, when used to correct coagulopathy range from 10-15 mL/kg. The plasma will be administered at a rate of 2-3 mL/kg/hr (140-210 mL/hr in a typical 70 kg adult). A research physician will be at bedside to follow patient resuscitation. Plasma administration may be terminated before the entire dose is administered if patients show clinical improvement, or if the treating clinician has concerns about circulatory overload. After the initial dose of plasma has

been given, subsequent fluid resuscitation (crystalloid or colloid) will be given at the discretion of the treating clinician.

The blood bank will have thawed plasma available on call as soon as an eligible patient has been identified. Type and screen will be performed concurrently to provide donor-matched plasma for subjects randomized to intervention group. For patients who proceed to the operating room during fluid resuscitation, the anesthesiology team will continue fluid administration per study protocol.

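### Asymptomatic VTE and delayed serological transfusion reactions are listed as assessed harms, but no visible section schedules a test for either, so a comparison between arms could reflect who was tested

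*Combined protocol and SAP*

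**What the plan says.** **Harms.** The outcomes text after Table 2 says that potential harms of plasma will be assessed. It names "symptomatic and asymptomatic venous thromboembolisms, transfusion-related allergic reactions, febrile non-hemolytic transfusion reaction, delayed-serological transfusion reactions", and also circulatory overload. Definitions are taken from a method of operation used in the group's earlier trials, which is not part of the document.

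**Data source.** Under Data Collection: "Data will be collected from the subject's medical record and the trauma registry". Appendix A (Hospital Information) has the entry "Complications (ARDS, AKI, venous thromboembolic events, sepsis, severe sepsis, septic shock, transfusion reactions, infections, multi-organ failure, pneumonia". It also lists laboratory results and diagnostic procedure results.

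**Scheduled tests.** "Biomarkers will be drawn at 0, 2, end of initial bolus of fluid administration, 6, 12, and 24 hours". The footnote to Table 2 gives the analytes, beginning "Serum biomarkers = syndecan-1, sTM, sFLT-1, VEGF, sRAGE, HMGB-1, IL-6, 8, 10, 1", and no red-cell antibody test is among them. For routine care: "Standard labs for critically ill patients (such as complete blood count, basic metabolic panel, and arterial blood gases) will be obtained per STICU protocol". Under Intervention, the one blood-bank test named is this: "Type and screen will be performed concurrently to provide donor-matched plasma for subjects randomized to intervention group". The only ultrasound named, under Endpoints of Resuscitation, is for inferior vena cava collapsibility.

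**Blinding.** "The healthcare provider will not be able to be blinded to the study intervention". Outcome assessors are blinded when feasible; laboratory technicians and statisticians are blinded.

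**Analysis.** Statistical Analysis gives relative risks with 95% confidence intervals for binary outcomes, and Bayesian probabilities of benefit and harm for the primary and secondary outcomes. Sample Size promises estimates and intervals for all measures, to inform a larger trial. Neither section has a rule for patients in whom a harm was never looked for.

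**The concern.** Both harms are silent. Asymptomatic VTE is seen only if a patient without signs is imaged, and a delayed serological reaction only if the antibody screen is repeated after transfusion. If neither is scheduled, the record holds only what was found through testing that clinicians chose to order, and those clinicians know the arm. They might image plasma patients more often because clotting is a named harm of plasma, or less often for other reasons. The direction cannot be predicted, so a reader cannot allow for it.

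Two results are at risk. A relative risk for VTE that includes asymptomatic events could show a difference in imaging practice. A zero count of delayed reactions could look more reassuring than the number re-screened supports. Adverse events belong to Specific Aim 3, a risk/safety evaluation is planned at 13 randomized patients, and the probabilities of harm are meant to inform the next trial. The absence of formal hypothesis testing does not help, because the problem is bias in an estimate and a confidence interval does not reveal it.

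**Working it through.** The plan states no event rate, testing rate or power for these harms, so there is no figure of its own to reproduce. The check has a textual part and an illustration.

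**1. Is a test scheduled for either harm?**

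| Harm | Needs | What the visible text provides |
|---|---|---|
| Asymptomatic VTE | Imaging without clinical signs | No imaging for VTE; ultrasound only for vena cava collapsibility |
| Delayed serological reaction | Repeat antibody screen after transfusion | One type and screen for plasma matching; no repeat; study draws are biomarkers only, to 24 h |

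No follow-up window is stated for either harm.

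**2. What happens to an untested patient?** The documents do not say. Collection is from the chart, complications are listed as events, the model for binary outcomes is relative risk, and no missing-data rule is given. The default is therefore that no recorded event becomes no event. This is an inference, and steps 3 and 4 depend on it.

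**3. Effect on the relative risk.** Let p be the true risk and t the share tested in an arm. Suppose testing is unrelated to true status, a test finds every event, and untested patients count as event-free. Then

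observed risk = p × t, and observed RR = (p_plasma / p_control) × (t_plasma / t_control).

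Illustration with assumed inputs: p = 15% in both arms, t = 60% and 30%.

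- 0.15 × 0.60 = 9.0%; 0.15 × 0.30 = 4.5%; RR = 2.0 with no true difference.
- With the testing shares reversed, RR = 0.5.
- With equal testing shares, RR = 1.0, whatever the common share.

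**4. Effect on the chance of seeing no event among 13 plasma patients.** The formula is (1 − p × t)^13, with assumed p.

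| True risk | All tested | Half tested |
|---|---|---|
| 10% | 25% | 51% |
| 20% | 5.5% | 25% |
| 30% | 1.0% | 12% |

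**5. What a zero count supports.** The exact two-sided 95% upper limit for 0/m is 1 − 0.025^(1/m), where m is the number actually tested.

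- m = 13: 24.7%
- m = 10: 30.8%
- m = 7: 41.0%
- m = 4: 60.2%

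Only 13, the planned arm size, comes from the documents; the other values of m are assumptions. For m below 13 the limit describes the whole arm only if the tested patients are representative of it, and patients chosen by clinicians may not be.

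**The case against.** **No scoring rule is written.** A reader might infer that the plan counts untested patients as event-free. It does not say so; Statistical Analysis names a model and sets no denominator. This stands, which is why the point is put as the default outcome of the plan.

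**Harm capture does not end at 24 h.** A reader might take Table 2 as the safety schedule. It is the biomarker schedule. Appendix A collects laboratory results, diagnostic procedure results and discharge data without a 24 h limit. This stands, and it means that tested counts can be taken from data already planned.

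**Controls may have a baseline screen.** A reader might infer that controls have none, because type and screen is described for the plasma arm. The text gives the purpose of that test and does not say controls go without. Co-interventions provides for red-cell transfusion in both groups. This stands.

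**A schedule may exist elsewhere.** The sentence after Table 2 has lost its beginning in the PDF reading, and the method of operation cannot be seen. This stands as a limit on the finding. The method of operation is, however, cited for definitions, not for surveillance.

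**The bias would be lost in noise.** With the assumed 9.0% and 4.5%, 13 per arm gives 1.17 and 0.585 expected events. A Wald interval at those values runs from about 0.1 to 42. The chance that at least one arm has no event is 0.91^13 + 0.955^13 − (0.91^13 × 0.955^13) = 0.294 + 0.550 − 0.161 = 68%. This is right and limits the practical weight. It also argues for descriptive reporting of these harms.

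**Blinded assessors.** They do not solve the problem, since they can judge only the tests that were ordered.

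**Conclusion.** The point holds in limited form. Two harms that need a test are named as assessed, no visible section schedules that test, and the plan calls for relative risks and probabilities of harm. A between-arm difference in these harms could therefore reflect testing rates, and a zero could look more reassuring than the number tested supports.

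The size is unknown. The ratio of 2.0 only restates an assumed twofold difference in imaging, and the limit of 60.2% assumes that 4 patients were re-screened; neither predicts what the trial will show. The 24.7% limit for 0/13 is exact but valid only if all 13 were tested. The conclusion rests on the inference about untested patients, on testing being unrelated to true status, and on there being no surveillance schedule in text that cannot be seen.

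The point is minor. It concerns secondary harms in a 26-patient pilot without formal testing. It does not affect the biomarker outcome, and it does not show that the plan will produce a false harm signal or a false reassurance, only that it could not be told apart from a true result.

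**What to change.** If the method of operation already sets systematic testing for both harms in both arms, cite it in the harms sentence; nothing more is needed. Otherwise, change the harms sentence and Statistical Analysis as follows.

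1. Make symptomatic, objectively confirmed VTE the between-arm VTE comparison. State that this reduces detection bias but does not remove it, because confirmation still depends partly on tests ordered by unblinded clinicians.
2. Report incidentally found asymptomatic VTE and delayed serological reactions descriptively, with no relative risk and no probability of harm.
3. For each arm, give the number imaged for VTE and the number with a repeat antibody screen, and show the remaining patients as *not assessed*. Take both counts from the laboratory and diagnostic procedure results already listed in Appendix A.
4. Note beside these counts that the tested patients were selected clinically, so a rate or limit among them may not describe the whole arm.

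The cost is a few sentences of wording and two counts per arm, with no new procedure. The downside is fewer events in the VTE comparison, wider and less reassuring limits for delayed reactions, and no formal contrast for two listed harms.
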